4.3 JUSTIFICATION FOR INTERVENTION

Justification for the mode of intervention delivery. RE-PACT uses a dynamic Just-in-Time Adaptive Intervention (JITAI) design.¹⁷ Though causes of respiratory illness in severe CP are modifiable, they are also broad and require distinct responses, even for the same child over time. RE-PACT's design addresses child and family changing needs. Managing crises with just-in-time action planning and bringing coaching directly to families breaks down barriers between home and clinical settings precisely when it matters most. This approach is innovative since we tailor the intensity of response (e.g., phone call, clinic visit, etc.) to family- and illness-specific needs. The adaptive nature of the intervention ensures it meets caregiver needs for that particular illness, whether requiring purely respiratory or a mix of respiratory and non-respiratory chronic disease management (e.g., seizures, feeding intolerance, etc.). The number and frequency of contacts is rooted in prior research using a related trial as well as feedback from families pilot-testing our texting tool. There is no minimum-acceptable participation in, or exposure to the intervention since the study is designed to assess feasibility, acceptability, and fidelity, i.e., varying rates of participation will be a relevant endpoint in itself.

4.4 END-OF-STUDY DEFINITION

A participant is considered to have completed the study if he or she has completed the baseline assessment, and the 6-month follow-up assessments, as shown in the Schedule of Activities (SoA), **Section 1.3.**

5 STUDY POPULATION

5.1 INCLUSION CRITERIA

The participant is the caregiver of a child with severe cerebral palsy. Individuals must meet all of the inclusion criteria in order to be eligible to participate in the study:

Caregiver Criteria

- Be at least 18 years of age
- Primary caregiver to an eligible child (child criteria below)
- Speak English or Spanish well enough to be interviewed
- Have a phone capable of sending/receiving text messages

Child Criteria

- Ages 0-17 years
- Have Gross Motor Function Classification System level IV or V Cerebral Palsy
- Cared for by respiratory specialist or receive daily respiratory treatments (oxygen, ventilation, airway clearance device, medications)

5.2 EXCLUSION CRITERIA

An individual who meets any of the following criteria will be excluded from participation in this study:

1. Lack of interest in text messaging or coaching interactions during the study

5.3 LIFESTYLE CONSIDERATIONS

During this study, participants are asked to:

- Reply to text messages when received at random times during daytime hours.
- Connect with an intervention coach either at home, in-person at a mutually agreeable location, by phone, or over the internet

5.4 SCREEN FAILURES

Screen failures are defined as participants who consent to participate in this study but are not subsequently assigned to the study intervention or entered in the study. Individuals who do not meet the criteria for participation in this trial (screen failure) because of meeting one or more exclusion criteria that are likely to change over time may be rescreened. Examples include child's development of needs for respiratory treatment, re-assignment to a GMFCS status that meets inclusion criteria,

acquisition of a phone capable to send/receive text messages. Rescreened participants will be assigned the same participant number as for the initial screening.

5.5 STRATEGIES FOR RECRUITMENT AND RETENTION

Recruitment

We will recruit caregivers of children with severe CP between 0-17 years old. We will recruit a total of n=90 participants (n=45 at each site) divided across 3 waves. In each wave, there is a 1-2 month enrollment period. We anticipate approximately 80% of those screened will enroll, requiring approximately 110 individuals to be screened.

Potential participants will be identified by reviewing the clinic registries and/or EHR data using diagnostic codes for CP (ICD-10 G80-83), which contain detailed information about children and their diagnoses. We will send an “opt-out” letter that alerts families that a research study is being conducted and their child may be eligible, with a contact number to call if they wish to opt out of the research or if they wish to receive additional information or have any questions. Potentially eligible caregivers will be contacted by phone to screen for eligibility and interest.

If the research team is not notified that a family wishes to opt-out the research, the study research personnel will attempt to call the families (or meet them at an upcoming visit) to complete screening, informed consent, baseline questionnaires and random group assignment. Eligibility criteria for caregivers are detailed in **Study Population, Section 5.1-5.2**, and include being self-identified English- or Spanish-speaking caregivers of children with severe CP who have respiratory needs. CP status and additional eligibility criteria will be determined with a reliable and valid parent questionnaire and screener conducted at the beginning of initial phone contact.

Retention and Incentives

Study participants in this pilot RCT will be contacted at baseline (enrollment), monthly (for intervention subjects), and at 6 months (intervention and control groups). While we expect some degree of attrition will be inevitable, we will work to minimize attrition by sending regular follow-up post cards and phone calls requesting updates in contact information and also confirming or updating contact information when child medical records are reviewed. Moreover, participants will receive \$100 on study entry and exit.

Inclusion of Women and Minorities

While we will not specifically recruit study participants based on gender, race or ethnicity, the demographics of our clinics are such that we expect parents to be predominantly women (mothers of young children brought to the clinic for care). At UCLA, families are predominantly Hispanic or Latino. Child participants will most likely be close to 50% male and 50% female. Together, we estimate approximately the demographic composition to be 35% Hispanic or Latino, 65% approximately distributed between white, non-Hispanic, African American (including a subset of Hispanic or Latino origin) and Asian, Pacific Islander, Native American, and multiracial groups combined. From the total 90

participants, we estimate 43 males and 47 females, 32 to identify as Hispanic and 58 non-Hispanic, and approximately 65 to identify as white, 9 as black, 5 as more than one race, and 11 as other (e.g., Asian, Pacific Islander, Native American, and unknown or not reported).

We also know that the majority of the Hispanic or Latino families are Spanish-speaking and will ensure that study materials are linguistically appropriate. Due to limitation of study resources, we must exclude families unable to speak English or Spanish well enough to be interviewed and receive care materials written in either English or Spanish.

We will collect demographic information about children and families as part of our data collection. While we anticipate that the intervention and control groups will be similar due to random assignment, we will adjust for any variables in our analysis that are not equal between the groups given the small sample size. In addition, we will analyze for any effect of primary home language on the study outcomes, as this may affect families' ability to navigate systems of care in the U.S.

Inclusion of Children/ Inclusion Across the Lifespan

Research participants for this study will include children and their parents or legal guardians. We propose to enroll 90 children between ages 0-17 years into this study and follow their health and health care for 6 months. This sample size and timeframe will sufficiently meet the need to establish trial protocol feasibility, acceptability, and fidelity and collect preliminary data for power calculations (it is intentionally not designed to be large enough to prove efficacy of the intervention). Although the entire proposed study relates specifically to children, we expect actual participation of children themselves to be minimal. Child-level data will be collected primarily using parent report and medical record review, with no direct child responses. Parents will be asked to provide consent for themselves and permission for their children to participate, including for the collection of child-level data. Children with severe cerebral palsy typically have functional and/or development limitations of such severity that they are not considered able to provide assent, so only parental permission will be obtained for this study, which involves minimal risk. We have the expertise and facilities to work with children of all ages and developmental abilities. Our research team includes senior researchers with pediatric clinical trials experience. Our clinical team is located at two major tertiary children's hospitals (American Family Children's Hospital / University of Wisconsin and Mattel Children's Hospital / UCLA) that specialize in delivering care to children and families facing this particular clinical condition. There is no upper age limit for parents or legal guardians to participate, and it is reasonable to expect that some older adults will be guardians for children in this study.

Justification for Inclusion of Vulnerable Subjects

Children of all ages with severe CP and see a respiratory specialist and/or use daily respiratory treatment will be included because those are the children with active disease who are most likely to have relevant fluctuations in health such that they will experience, and benefit from, intervention activities. Finally, we only have resources to recruit and interview families in English or Spanish.

6 STUDY INTERVENTION(S) OR EXPERIMENTAL MANIPULATION(S)

6.1 STUDY INTERVENTION(S) OR EXPERIMENTAL MANIPULATION(S) ADMINISTRATION

6.1.1 STUDY INTERVENTION OR EXPERIMENTAL MANIPULATION DESCRIPTION

The Respiratory Exacerbation Plans for Action and Care Transitions (RE-PACT) intervention has three primary activities: (1) mHealth surveillance of parent confidence to avoid hospitalization, (2) respiratory illness action planning, and (3) just-in-time adaptive coaching response triggered by low confidence or hospitalization. The theoretical basis of the intervention includes efficacy of the initial PACT trial, and prior research on preventing hospitalizations combined with behavioral intervention theory which suggests that decisions to seek care (behaviors) are influenced by capability (family capacity), opportunity (health system and susceptibility), and motivation (confidence). Confidence is a modifiable expression of self-efficacy to achieve an outcome, i.e., to avoid hospitalization and manage (respiratory) crisis at home. In our earlier work, low confidence predicted hospitalization.

Participants randomized into the intervention will receive initial T_0 intervention activities (mHealth monitoring and respiratory action plan) by phone, at clinic, or during a hospitalization within one month of enrollment.

mHealth surveillance. Upon enrollment, families will begin receiving weekly text messages asking them to rate their confidence (1-10) for their child to avoid a hospitalization in the next month.

Action Planning. The action and format are adapted from the original PACT study, and contents include (at minimum) recognizing, describing and managing the child's known contributors to respiratory illness. In step 1, objective and subjective indicators of baseline ("green"), concerning ("yellow"), and severe ("red") statuses are defined (e.g., >2 L/min of oxygen). In step 2, the specific actions caregivers should take to manage each status are defined (e.g., increase vest, albuterol, suction to q4, use oxygen up to 4 L/min).

Just-in-time Adaptive Coaching Intervention Response. Coaching is accomplished by adapting PACT, which was initially adapted from the Care Transitions Intervention® (CTI),⁵⁰ to the pediatric population. The focus is: (1) medication self-management, (2) patient-centered records maintained by families, (3) timely follow-up, and (4) "red flags" and instructions how to identify/respond to them (i.e., action plans). Face-to-face visits are typically at the family's home; however, a neutral or "virtual" (telephone) visit is an option. Coaches review the four components, elicit goals, and focus coaching activities on needs identified by families. Phone calls discuss progress toward goals. This coaching approach provides the structure for JITAI activities.

Control Group. Those participants randomized to the control group will be provided usual care through the comprehensive clinical program at their children's hospital. They will also complete pre- and post-study assessments.

6.1.2 ADMINISTRATION AND/OR DOSING

mHealth Surveillance. Text messages are programmed to be sent at random days / times to caregivers beginning the Monday after enrollment. Text messages average once weekly (Sun-Thurs) between 8AM and 9PM (local time). After 2 hours of non-response, a reminder is sent, and this is repeated up to 2 times.

Action Planning. All intervention families receive respiratory illness action plans within 1 month of study entry, and just-in-time plans are also created at times of low confidence. Plans are created in caregivers' preferred language (English, Spanish) by physician or nurse practitioner using our protocol (see intervention manual). After plans are created, teach-back is used. Copies are given to families and included in medical records. Plans are discussed at weekly clinical meetings for clarity and accuracy.

Just-in-time Adaptive Coaching Intervention Response. In the original design, coaches met families prior to a hospital discharge, conducted face-to-face visits within 72 hours and 3 phone calls within 30 days, post-discharge. Compared to the original PACT design, RE-PACT was adapted to trigger just-in-time adaptive intervention (JITAI) action planning and coaching doses when caregiver text message responses indicate low confidence. JITAI action planning and coaching doses occur within 24 hours of any text message ratings ≤ 4 . This confidence threshold to trigger JITAI and the text prompt wording was vetted in preliminary qualitative research with families and clinicians and is based on our prospective pilot study at UW and UCLA whereby confidence ratings ≤ 4 predicted hospitalizations a median (IQR) 8 (2-10) days in advance. The protocol currently supports intervention coach credentials to include undergoing coach training (or equivalent, see intervention manual), and individuals can possess any university degree of higher. For example, a coach could be a care coordinator with a bachelor's degree, a physician, or other health professional.

The study feasibility, acceptability and fidelity measures are designed to quantify intervention doses, dose intensity and frequency (e.g., # of coach visits, # of action plans), and include incomplete dose administration (e.g., poor text message response rates).

6.2 FIDELITY

6.2.1 INTERVENTIONIST TRAINING AND TRACKING

Action plans are created by study physicians or nurse practitioners using our worksheet-based protocol (see intervention manual). Plans are discussed at weekly clinical meetings for clarity and accuracy. For each enrollee, the study team will log whether (1) an action plan was created (and how many were created), (2) when they were created, and (3) whether/when each plan was reviewed with the clinical team. Spanish-speaking Action Plans will be drafted in Spanish by native-speaking Spanish clinicians or designated clinical translators.

Coaching interventionist training is based on the initial PACT protocol (see intervention manual), and includes an overview of coaching, scenarios and role-practice, mock sessions with feedback, supervisor observation with feedback, as well as weekly coaching peer discussions throughout the intervention period. The protocol currently supports intervention coach credentials to include any bachelor's degree of higher. For example, a coach could be a care coordinator with a bachelor's degree, a physician, or

other health professional. The study fidelity measures are designed to quantify coaching doses, dose intensity and frequency (e.g., # of coach visits), and include incomplete dose administration (e.g., missed coach visits / calls), etc.

6.3 MEASURES TO MINIMIZE BIAS: RANDOMIZATION AND BLINDING

Random allocation will be concealed to research staff conducting recruitment and will use a 1:1 allocation with random block sizes of 2 and 4. Block randomization will be achieved with a computer-generated random number list prepared by the study biostatistician having no clinical involvement in the trial. Randomization will be stratified by site (UW vs UCLA) to account for site-specific study characteristics. After the research team member obtains participant consent, they will telephone contact the study project manager who is independent from the recruitment process to receive the group assignment. Alternatively, it may be arranged that randomization will be built into the REDCap database by the study biostatistician.

Since this study aim is feasibility, acceptability and fidelity, there is no plan for whether/when to break randomization codes. Study and clinical team members cannot practically be blinded to treatment because only those randomized to intervention will receive text messages, specific action plans, and coaching. The need for clinical team members to create action plans and interact with coaches will identify those randomized to intervention. Presumably, the need for admission to the hospital for a respiratory illness and secondary clinical endpoints (ED visits, need for antibiotics, steroids, hospital days, and death) are less prone to observer bias. The outcome evaluator (study biostatistician) will remain blinded during analyses.

6.4 STUDY INTERVENTION/EXPERIMENTAL MANIPULATION ADHERENCE

Given the nature of this pilot RCT, participant adherence measures are delineated within the primary acceptability and fidelity outcomes for the study. These include attrition, monthly self-reported action plan and coaching use, response rates to text messaging and response rates to coaching visits and follow-up phone calls.

Loss to follow-up is defined in **Section 7.3, Lost to follow-up.**

6.5 CONCOMITANT THERAPY

For this protocol, participants may use existing action plans that have been created outside the study. Action plan existence/usage will be assessed at monthly study calls and documented in the relevant Case Report Form (CRF).

6.5.1 RESCUE THERAPY

The study site will not supply rescue medication.

7 STUDY INTERVENTION/EXPERIMENTAL MANIPULATION DISCONTINUATION AND PARTICIPANT DISCONTINUATION/WITHDRAWAL

7.1 DISCONTINUATION OF STUDY INTERVENTION/EXPERIMENTAL MANIPULATION

When a subject discontinues from any element of RE-PACT (action planning, texting, coaching), but not from the study, remaining study procedures will be completed as indicated by the study protocol.

The data to be collected at the time of study intervention discontinuation will include the following:

- The reason(s) for discontinuing the participant from the intervention, and methods for determining the need to discontinue
- If the participant is due to complete assessments within 2 weeks of being discontinued from the study intervention, those assessments will be administered at the time of discontinuation; if the next scheduled assessments are more than 2 weeks from the discontinuation date, the discontinued participant will wait for the next scheduled assessment. Thereafter, the participant will be included in all future scheduled assessments, even though not participating in the intervention.

7.2 PARTICIPANT DISCONTINUATION/WITHDRAWAL FROM THE STUDY

Participants are free to withdraw from participation in the study at any time upon request.

An investigator may discontinue a participant from the study for the following reasons:

- Significant study intervention non-compliance, unless varying compliance is an aspect of the study objectives
- Lost-to-follow up; unable to contact subject (see **Section 7.3, Lost to Follow-Up**)
- The participant meets an exclusion criterion (either newly developed or not previously recognized) that precludes further study participation
- If a subject is no longer a part of the complex care program at the UW or UCLA, their enrollment in the study will be discontinued.

The reason for participant discontinuation or withdrawal from the study will be recorded on the Discontinuation/Withdrawal Case Report Form (CRF). Subjects who sign the informed consent form and are randomized but do not receive the study intervention may be replaced. Subjects who sign the informed consent form, and are randomized and receive the study intervention, and subsequently withdraw, or are discontinued from the study, will not be replaced.

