4.2 SCIENTIFIC RATIONALE FOR STUDY DESIGN

Rational for the study design. Conducting this pilot study will provide a high degree of certainty that the final RE-PACT protocol is feasible, acceptable and can be delivered with fidelity. This is a critical approach to designing interventions that can be integrated in diverse, real-world, settings and sustained.

Using an RCT design (i.e., with a control group who do not receive intervention) is necessary to establish effect sizes needed to adequately power an efficacy trial. The findings from this study will allow precise estimation of effect sizes to conduct a fully powered, multisite hybrid Type 2 effectiveness-implementation RCT.

Rationale for the type and selection of control conditions. The control group will be randomly assigned, allowing the study team to conclude that endpoint differences between each group are most likely due to the intervention itself.

Potential problems associated with the control group. The control group may have pre-existing respiratory action plans created during routine clinical care. In addition, the coach may have difficulty avoiding contaminating the control group by inadvertently conducting coaching activities to those not assigned to the intervention group. This risk will be minimized since action plans using the study protocol will only happen for intervention subjects, and coaching is triggered only through mHealth text responses and texting will only be set up for those assigned to the intervention.

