10.1.1.2 CONSENT PROCEDURES AND DOCUMENTATION

All study participants will undergo informed consent including consent to view the child's medical record. In all informed consent materials, we will make clear to potential participants that their participation is voluntary, and they may choose to leave the study at any time. Potential participants identified from the clinic registry and, following an opportunity to opt-out of further contact, their interest and eligibility will be determined through a structured screening. If a family is interested in participation, they may contact the study team or a member of the study team will contact them for informed consent. Enrollment visits will be conducted either in person or remotely (via WebEx). All consent forms will be signed electronically using a REDCap form. If a family enrolls in person, study staff will supply an iPad on which to sign the consent form. If a family chooses to enroll remotely, study staff will send the family a REDCap survey link containing the consent form. All subjects will also receive a hard copy of the consent form for their records. Informed consent materials will be provided in private spaces in both written and verbal formats, will review in detail the study design, including random assignment to the intervention and control groups, potential risks of participation, protections against risk, and the rights of human research subjects. The informed consent process will also include review and signing of the HIPAA waiver, allowing researchers to review the child's medical records. Parents will be able to decline parts of the study and still participate in other parts, and can revoke their consent at any point.

Because this research involves children with severe cerebral, it is expected that all subjects will lack capacity to give meaningful assent. Assent will not be obtained.

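### Section 7.2 lets an investigator withdraw a randomised family for a newly developed exclusion criterion; the only one listed is lack of interest in texting or coaching, so follow-up can be lost mainly in the intervention arm

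*Combined protocol and SAP*

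**What the plan says.** Section 7.2 opens its list of reasons with "An investigator may discontinue a participant from the study for the following reasons". One reason is: "The participant meets an exclusion criterion (either newly developed or not previously recognized) that precludes further study participation". The withdrawal is from the study, not only from the intervention, and the section does not say that outcome collection by chart review continues afterwards.

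Section 5.2 has a single exclusion criterion: "Lack of interest in text messaging or coaching interactions during the study".

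Texting and coaching belong to one arm. Section 4.2 states that "coaching is triggered only through mHealth text responses and texting will only be set up for those assigned to the intervention", and Section 6.3 that "only those randomized to intervention will receive text messages, specific action plans, and coaching". Section 5.5 and the schedule in 1.3 give monthly contact to intervention families only. Controls are assessed at baseline and at month 6.

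Other sections treat disengagement differently:

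- Section 7.1, on a family that drops texting, action planning or coaching: "but not from the study, remaining study procedures will be completed as indicated by the study protocol".
- Section 4.3: "There is no minimum-acceptable participation in, or exposure to the intervention". It adds that variation in participation is of interest as an endpoint.
- Section 10.1.1.2: "Parents will be able to decline parts of the study and still participate in other parts". Section 2.3.3 says much the same about study components.
- Section 9.3 adopts intention-to-treat.
- The first reason in Section 7.2, significant non-compliance, is waived where varying compliance is among the study's objectives.

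**The concern.** A family that loses interest after randomisation falls under two rules. Under 7.1 it stops an element and stays in all later assessments. Under the exclusion-criterion ground in 7.2 it can leave the study. The choice rests with an investigator who knows the allocation, since 6.3 accepts that study and clinical staff cannot be blinded.

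A control family has no texts or coaching to lose interest in, and no scheduled assessment before month 6 that would show it. In practice the ground can therefore shorten follow-up of disengaged families in the intervention arm, while similar families in the control arm stay to the end. If disengaged families differ in their illness rate, the rate ratio that is meant to inform the larger trial is shifted by who remains under observation.

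Two primary measures in Section 3 are exposed as well. Refusal of a component would be recorded as study drop-out against the success limit of below 10%, and it would pull down mean enrolment duration, whose success value is 6 months.

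**Working it through.** **Text.** Three steps lead to the possible one-sided loss.

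1. 7.2 refers to exclusion criteria, and 5.2 lists only lack of interest in texting or coaching.
2. 4.2 and 6.3 confine texting and coaching to the intervention arm. 5.5 and 1.3 confine monthly contact to it.
3. The waiver for varying compliance is attached to the non-compliance ground only. The exclusion-criterion ground has no such waiver, so disengagement that the first ground leaves alone can still lead to withdrawal under this one.

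Section 7.3 does not settle the matter. Apart from families who leave the clinical program, it concerns families who cannot be reached, whereas a family that has lost interest may still be reachable.

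**Illustration of size.** The plan gives no figure to reproduce on this point.

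Inputs from Section 9.2: 45 per arm; one severe respiratory illness per child-year, which is 0.5 per 6 months. Section 9.4.3 defines the outcome as illnesses per person-month.

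Assumed, because the documents do not say: 5 of 45 intervention families are withdrawn at month t, their rate is k times the arm's mean, and the intervention has no effect. The ratio is intervention over control (the power table in 9.2 uses the inverse).

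- Control: 45 × 0.5 = 22.5 events in 45 × 6 = 270 person-months, or 0.0833 per month.
- Intervention events = (22.5 − 5 × 0.5k) + 5 × 0.5k × t/6.
- Intervention person-months = 40 × 6 + 5t.

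| k | t (month) | Events | Person-months | Rate | Apparent ratio |
|---|---|---|---|---|---|
| 2 | 0 | 17.5 | 240 | 0.0729 | 0.875 |
| 2 | 1 | 18.33 | 245 | 0.0748 | 0.90 |
| 2 | 3 | 20.0 | 255 | 0.0784 | 0.94 |
| 1 | any | – | – | 0.0833 | 1.00 |
| 0.5 | 0 | 21.25 | 240 | 0.0885 | 1.06 |
| 0.5 | 3 | 21.875 | 255 | 0.0858 | 1.03 |

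A wider grid lets a share d of 5% to 20% be withdrawn at month 0 to 3, with 0.5 to 3 times the rate of *engaged* families (here k is relative to those families):

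ratio = [((1−d)·6 + d·k·t) / ((1−d)·6 + d·t)] / [(1−d) + d·k]

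Its extremes are 1/(0.8 + 0.2 × 3) = 0.71 and 1/(0.8 + 0.2 × 0.5) = 1.11, both at d = 20% and t = 0.

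**Drop-out.** Below 10% of 90 allows at most 8 families. Five withdrawals are 5/90 = 5.6%.

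**Against sampling error.** With dispersion 1.0 (Section 9.2), about 40 per arm and a mean of 0.5, the variance of the log ratio is (1/0.5 + 1/0.5 + 2 × 1.0)/40 = 0.15, so the standard error is 0.39. A null estimate would have a 95% interval of about 0.47 to 2.1.

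**The case against.** A reader might infer that the protocol orders the removal of disengaged families, and only from the intervention arm. The documents do not support that, for four reasons.

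- **The rule is permissive.** The investigator may withdraw a family and need not.
- **The term is used more widely elsewhere.** Section 5.4 speaks of exclusion criteria and gives examples that are unmet inclusion criteria: respiratory need, GMFCS status and a suitable phone. On that usage the ground also covers eligibility errors or changes in both arms. A control family could also, in principle, be found to have lacked interest from the start.
- **The ground carries a qualifier.** The criterion must preclude further participation. Sections 7.1, 4.3 and 10.1.1.2 suggest that disengagement does not.
- **Section 5.2 may be meant for screening.** Section 8.1 checks interest and willingness to text at that stage, so the criterion can be read as a question about intended participation.

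On size, the effect estimate is a secondary aim of a pilot that states it is underpowered. A ratio of 0.90 to 0.94 is small beside an interval of 0.47 to 2.1. Section 9.4.3 also plans multiple imputation.

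Much of this stands, and it limits the point to what the rule can do. It does not remove it. The wider reading in 5.4 adds grounds without taking disengagement out. If loss of interest never precludes participation, nothing listed in 5.2 is left for the ground to act on. The intention-to-treat label does not recover outcomes that are no longer collected. Imputation is planned only as a sensitivity analysis, and it does not by itself remove bias from loss that depends on unobserved outcomes.

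**Conclusion.** The point holds as an inconsistency that permits avoidable, mainly one-sided loss of follow-up. Sections 5.2 and 7.2 together allow an unblinded investigator to withdraw a disengaged intervention family, and this cannot be squared with 7.1, 4.3, 2.3.3, 10.1.1.2 and 9.3.

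The size and direction of any bias cannot be fixed from the documents. The ratio of 0.875 should not be read as the expected bias. It needs withdrawal at month 0, 5 of 45 families, twice the arm's mean rate and no true effect. Interest lost through experience of the intervention is lost later, and the same inputs then give 0.90 at month 1 or 0.94 at month 3. Equal rates give 1.00, and lower rates in the withdrawn families move the ratio above 1.

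The effect on the drop-out measure does not depend on illness rates: each such withdrawal counts against the limit of 8 in 90. The correction is worth making because it costs almost nothing. The case for it rests on the conflict between sections, not on the illustration.

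**What to change.** Keep the ground in 7.2 for eligibility errors. Deleting it would also remove the route for ineligibility discovered late in either arm. Make two additions:

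- In 5.2: *This criterion is applied before randomisation only.*
- In 7.2: *Loss of interest in texting, action planning or coaching after randomisation is discontinuation of an intervention element under Section 7.1, not withdrawal from the study. Chart-based outcomes and the month-6 assessment continue unless consent is withdrawn.*

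The cost is one short addition to each section. Chart review of these children continues under the medical-record authorisation already obtained (4.1, 10.1.1.2), and the month-6 assessment is already scheduled for both arms.
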